10.1.1. Subgroup Analysis

It is clinically considered that sex and co-morbidities (diabetes or renal dysfunction) can affect the change in pain. A two-factor ANOVA with treatment and one of the covariates (sex, diabetes, or renal dysfunction) as the factors will be used to analyze the primary endpoint. For each analysis, treatment group, covariate, and treatment group by covariate interaction will be included in the model. If the treatment by covariate interaction is judged to be insignificant ($p > 0.10$) then the interaction term will be removed from the model and pairwise treatment comparisons of adjusted means vs. Placebo using Dunnett's test will be presented. If the treatment by covariate interaction term is significant, then separate analyses will be performed for the different levels of the covariate of consideration.

10.1.2. Imputation Methods of VAS Results for the ITT Population

In order to include all subjects in the ITT population, the following imputation rules will be applied for analysis of the ITT population.

For subjects without the primary efficacy endpoint (VAS change from baseline to 9 months), the following imputation methods will be applied:

- For missing Baseline VAS, assign the VAS score at Screening if the VAS score at Day 0 is missing.
- For missing 9 month VAS, assign the 12 month VAS score if the 9 month VAS is missing.

- For missing 9 month VAS, assign the last reported VAS prior to the 9 month VAS visit if both the 9 month and 12 month VAS assessments are missing.

For subjects who had a major amputation or limb procedure carried out, the following imputation methods will be applied:

- For subjects with a major amputation, assign the post baseline VAS score prior to the amputation.
- For subjects with a limb salvage, assign the post baseline VAS score prior to the intervention.

10.2. Secondary Efficacy Variables

The analyses for the secondary efficacy variables will be performed based on the Per-Protocol Population and ITT Populations. The secondary efficacy endpoints include:

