5.1. Visit Windows

Data at each scheduled follow up visit will be analyzed according to the nominal visit identified on the CRF, regardless of the actual elapsed time since treatment.

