6. ANALYSIS POPULATIONS

The following subject populations will be used for analysis:

The Intent-to-Treat (ITT) population will include all subjects who were randomized regardless of whether treatment was received. Subjects will be analyzed according to the treatment to which they were randomized.

The Safety population will include all subjects who receive at least one dose of study drug medication and data will be analyzed according to the treatment actually received. The safety analyses will be performed on the Safety population.

The per-protocol (PP) population will include all subjects who received the correct dose of study drug medication, have the 9-month VAS assessment, and do not have any protocol violations or major deviations as determined by Medical Monitoring. The per-protocol population will be determined in a blinded review before database lock. Subjects will be analyzed according to the treatment to which they were randomized. Primary efficacy analyses will be performed on the PP population.

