10.2.7. Amputation and Mortality Rate

The rates of amputation, limb salvage and mortality will be analyzed for all treated subjects per actual treatment using the method for time-to-event variables. The probability of being event-free at 6 and 12 months will be summarized for each treatment arm and compared vs. Placebo using a Log Rank test.

The duration of time to amputation will be defined as the number of days between the day of amputation – the first dose date + 1. If a subject does not report amputation, then the date that the subject will be censored at the date of study discontinuation. If the date of study discontinuation is not available, then the subject's censor date will be the last known visit the subject attended. The same calculation will be repeated for limb salvage and mortality (time to death).

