6.2.2.2	Transcutaneous Oxygen Pressure Assessment- TcPO ₂ Ratio - Posterior Calf (ITT Population)
6.2.3.1	Transcutaneous Oxygen Pressure Assessment- TcPO ₂ Ratio- Dorsum Foot (Per-Protocol Population)
6.2.3.2	Transcutaneous Oxygen Pressure Assessment- TcPO ₂ Ratio - Dorsum Foot (ITT Population)
7.1.1	Ankle Brachial-Index – Index Leg (Per-Protocol Population)
7.1.2	Ankle Brachial-Index – Index Leg (ITT Population)
7.2.1	Ankle Brachial-Index – Non-Index Leg (Per-Protocol Population)
7.2.2	Ankle Brachial-Index – Non-Index Leg (ITT Population)
8.1.1	Toe Brachial-Index – Index Leg (Per-Protocol Population)
8.1.2	Toe Brachial-Index – Index Leg (ITT Population)
8.2.1	Toe Brachial-Index – Non-Index Leg (Per-Protocol Population)
8.2.2	Toe Brachial-Index – Non-Index Leg (ITT Population)
9.1.1	Wound Area (Per-Protocol Population)
9.1.2	Wound Area (ITT Population)
9.2.1	Categorical Analysis of Wound Healing (Per-Protocol Population)
9.2.2	Categorical Analysis of Wound Healing (ITT Population)
10.1.1	VascuQoL – Activity (Per-Protocol Population)

10.1.2	VascuQoL – Activity (ITT Population)
10.2.1	VascuQoL – Symptom (Per-Protocol Population)
10.2.2	VascuQoL – Symptom (ITT Population)
10.3.1	VascuQoL – Pain (Per-Protocol Population)
10.3.2	VascuQoL – Pain (ITT Population)
10.4.1	VascuQoL – Emotional (Per-Protocol Population)
10.4.2	VascuQoL – Emotional (ITT Population)
10.5.1	VascuQoL – Social (Per-Protocol Population)
10.5.2	VascuQoL – Social (ITT Population)
10.6.1	VascuQoL – Total (Per-Protocol Population)
10.6.2	VascuQoL – Total (ITT Population)
10.7.1	VascuQoL- By Individual Question (Per-Protocol Population)
10.7.2	VascuQoL- By Individual Question (ITT Population)
11.1.1	Amputation – Event-Free Probability (Per-Protocol Population)
11.1.2	Amputation – Event-Free Probability (ITT Population)
11.2.1	Limb Salvage – Event-Free Probability (Per-Protocol Population)
11.2.2	Limb Salvage – Event-Free Probability (ITT Population)
11.3.1	Mortality – Event-Free Probability (Per-Protocol Population)
11.3.2	Mortality – Event-Free Probability (ITT Population)
12.1	Rutherford Classification of Disease Severity (Per-Protocol Population)
12.2	Rutherford Classification of Disease Severity (ITT Population)
13	Study Drug Exposure(Safety Population)
14	Treatment Emergent Adverse Events by System Organ Class and Preferred Term (Safety Population)
15	Treatment Emergent Adverse Events by Maximum Severity (Safety Population)

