Number (%) of Subjects Who Expired	n (%)	n (%)	n (%)
Number (%) of Subjects Censored	n (%)	n (%)	n (%)
Quartiles [95% CI] (days)			
25 th Percentile	xx (xx.x, xx.x)	xx (xx.x, xx.x)	xx (xx.x, xx.x)
50 th Percentile	xx (xx.x, xx.x)	xx (xx.x, xx.x)	xx (xx.x, xx.x)
75 th Percentile	xx (xx.x, xx.x)	xx (xx.x, xx.x)	xx (xx.x, xx.x)
p-value ^[1]		x.XXXX	x.XXXX
Kaplan Meier Estimate (# at Risk)			
6 Months	x.XXXX (n)	x.XXXX (n)	x.XXXX (n)
12 Months	x.XXXX (n)	x.XXXX (n)	x.XXXX (n)
Range (days)			
Subjects with an Event	xx, xx	xx, xx	xx, xx
All Subjects	xx, xx	xx, xx	xx, xx

^[1] P-value test for treatment difference using log rank test.
path\t_program.sas date time

Programmer Note Tables 11.1.2 will be identical to Table 11.1.1 for the ITT Population.
Programmer Note For censoring rules, see Section 10.2.7 of the Statistical Analysis Plan.

Table 12.1
Rutherford Classification of Disease Severity
Per-Protocol Population

	Placebo (N=)		VM202- 8 mg (N=)		VM202- 16 mg (N=)	
	Result	Change ^[2]	Result	Change ^[2]	Result	Change ^[2]
Baseline^[1]						
N		n xx.x (xx.xx)		n xx.x (xx.xx)		n xx.x (xx.xx)
Mean (SD)		xx.x		xx.x		xx.x
Median		xx, xx		xx, xx		xx, xx
Min, Max						
6 Months						
N		n xx.x (xx.xx)	n xx.x (xx.xx)	n xx.x (xx.xx)	n xx.x (xx.xx)	n xx.x (xx.xx)
Mean (SD)		xx.x	xx.x	xx.x	xx.x	xx.x
Median		xx, xx	xx, xx	xx, xx	xx, xx	xx, xx
Min, Max						
Comparison vs. Placebo						
Model 1^[3]						
LS Means (SE)			xx.x (xx.x)		xx.x (xx.x)	xx.x (xx.x)
LS Mean Differences (SE)					xx.x (xx)	xx.x (xx)
95% CI for LS Mean Differences					(xx.x, x.xx)	(xx.x, x.xx)
Overall p-value for Treatment Differences						
Pairwise p-value vs. Placebo (Dunnett's test)					x.XXXX	x.XXXX
Baseline vs. 6 Months (Paired t-test)		x.XXXX		x.XXXX		x.XXXX
Model 2^[4]						
Overall p-value for Treatment Differences (Jonckherre-Terpstra test)					x.XXXX	x.XXXX
Pairwise p-value vs. Placebo (Wilcoxon Rank Sum test)					x.XXXX	x.XXXX
Baseline vs. 6 Months (Wilcoxon Signed Rank test)		x.XXXX		x.XXXX		x.XXXX

^[1] Baseline defined as the last non-missing value prior to first dose of study drug.

^[2] Change = Change from Baseline

^[3] One-way analysis of variance (ANOVA) with treatment group as a factor.

^[4] Nonparametric tests for differences across a one-way classification of treatment.

path\t_program.sas date time

Programmer Note Repeat for all available time point, 6mo, 9mo and 12mo.

Programmer Note Tables 12.2 will be identical to Table 12.1 for the ITT Population.

Table 13

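### The per-protocol mortality table (SAP Table 11.3.1) must show 6-month survival of 1.0000 in every arm, and the per-protocol event tables conflict with the all-treated population in SAP 10.2.7

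*SAP*

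**What the plan says.** Protocol 6.2.2 names mortality at six and twelve months after first treatment as a secondary endpoint. The SAP then gives two answers on who is analyzed.

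- **General rule (SAP 10.2).** "The analyses for the secondary efficacy variables will be performed based on the Per-Protocol Population and ITT Populations". Appendix A follows it with three PP tables (11.1.1 amputation, 11.2.1 limb salvage, 11.3.1 mortality) and three ITT counterparts. Table 11.3.1 is listed as "Mortality – Event-Free Probability (Per-Protocol Population)". Its Appendix B layout has rows at 6 and 12 months under "Kaplan Meier Estimate (# at Risk)", with log-rank p-values against placebo.
- **Specific rule (SAP 10.2.7).** "The rates of amputation, limb salvage and mortality will be analyzed for all treated subjects per actual treatment". Figure 1 in Appendix C is laid out for the Safety population, and a note extends that layout to Figures 2 and 3. Appendix A lists no Safety version of Tables 11.x.

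SAP 6 defines the sets. "The per-protocol (PP) population will include all subjects who received the correct dose of study drug medication, have the 9-month VAS assessment", with further exclusions for protocol violations and major deviations. ITT covers "all subjects who were randomized regardless of whether treatment was received". Both sets are analyzed by randomized arm. SAP 10.1.2 fills in a missing 9-month VAS, but only for ITT: "the following imputation rules will be applied for analysis of the ITT population". The 9-month visit window is plus or minus one month (Protocol Appendix 1).

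**The concern.** Membership of the PP set depends on something that happens about nine months after the first dose and requires the subject to be alive. Using that set to estimate survival at six months means that the answer is known before any data are seen. The 12-month estimate leaves out every death before the 9-month VAS.

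Amputation and limb salvage are affected less. An amputee can still give a 9-month VAS, so those PP estimates are not fixed, but they are selected on being alive and assessed at month 9.

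At stake are a table with p-values for a named endpoint whose first row carries no information, and a programmer who cannot satisfy 10.2, 10.2.7, the table shells and the figure layouts together. SAP 10 makes PP the primary efficacy population, so the uninformative version stands first in each pair.

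**Working it through.** The plan gives no figure to reproduce here. The main result is a matter of definitions; the arithmetic only shows scale.

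**Step 1: the 6-month row**

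1. A PP subject has an observed 9-month VAS (SAP 6). Imputation cannot supply one, because it is confined to ITT (SAP 10.1.2).
2. The 9-month window opens at month 8, so an in-window VAS falls after the 6-month landmark. Every PP subject was alive then.
3. SAP 10.2.7 censors at study discontinuation or, failing that, at the last visit attended. A subject who attended the 9-month visit is not censored before it.
4. So by month 6 the PP set has no deaths and no censoring. The Kaplan-Meier estimate is 1.0000 and the number at risk equals PP N, in every arm.

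There is one exception. SAP 5.1 analyzes visits "according to the nominal visit identified on the CRF, regardless of the actual elapsed time since treatment". A visit labelled 9-month but held before month 6, more than two months outside its window, would break step 2.

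**Step 2: scale, for illustration only**

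Let m be 12-month mortality with a constant hazard, so F(t) = 1 − (1 − m)^(t/12). Protocol 1.3.3 gives mortality of about 25%, and up to 45% after amputation. It attaches no explicit period to the 25%, so reading it as 12-month mortality is an assumption; 10% is a further assumption. The trial excludes subjects with life expectancy under 6 months and severe or recent cardiac disease, so the background rates may not transfer. PP values take the VAS at month 9.

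| Quantity | m = 10% | m = 25% | m = 45% |
|---|---|---|---|
| All-treated 6-month mortality, F(6) | 5.1% | 13.4% | 25.8% |
| PP 6-month mortality | 0% | 0% | 0% |
| F(9) | 7.6% | 19.4% | 36.1% |
| PP 12-month mortality, (m − F(9))/(1 − F(9)) | 2.6% | 6.9% | 13.9% |
| Expected deaths after month 9 in 50, 50(m − F(9)) | 1.2 | 2.8 | 4.4 |
| Same for one dose arm plus placebo, 30(m − F(9)) | 0.7 | 1.7 | 2.7 |

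At m = 25%, moving the VAS to month 8 or month 10 changes PP 12-month mortality to 9.1% or 4.7%. The counts ignore replacement of early dropouts (Protocol 3.5.2). They are taken before the other PP exclusions, which can only lower them.

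**Step 3: a lower early hazard**

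If the hazard in months 0 to 6 is half the later hazard, then G(t) = 1 − exp(−H(0.5·min(t, 6) + max(t − 6, 0))/9), with H = −ln(1 − m). For m = 10% and 25%, G(6) is 3.5% and 9.1%, and expected deaths after month 9 in 50 are 1.6 and 3.8. The PP 6-month figure stays at 0%.

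**Step 4: can the tables agree?**

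Yes, if no early death occurs. Under constant hazard, a 10-subject arm has no death by month 6 with probability (1 − F(6))^10 = 0.59 at m = 10% and 0.24 at m = 25%. No death by month 9 among all 50 has probability (1 − F(9))^50 = 0.019 at m = 10% and 0.00002 at m = 25%.

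**The case against.** The best defence is that 10.2.7 names its own population and a specific section normally governs a general lead-in. On that reading the intended analysis is already right, Figures 1 to 3 follow it, and ITT Table 11.3.2 gives 6- and 12-month mortality free of the 9-month condition. This limits the harm but does not remove the problem: the shells implement 10.2, and no all-treated table is listed.

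Other parts of the defence stand.

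- **Actual against randomized arm.** A reader might see a second conflict here for PP. It is largely nominal, because PP requires the correct dose. The difference matters for ITT.
- **Hidden deaths.** A reader might infer that early deaths vanish from the report. They do not: those recorded in treated subjects appear in ITT Table 11.3.2, Figure 3 and Listing 40. The opposite claim, that every death is kept, is also too strong. Deaths after discontinuation may not be captured, and untreated subjects have no first-dose date from which to count time.
- **Expected counts are not ceilings.** At m = 25% the expected 2.8 deaths after month 9 is an average. With 50 subjects and probability 0.0559 each, three or more deaths has probability 1 − (0.056 + 0.167 + 0.242) = 0.535.
- **Amputation and limb salvage.** The argument is weaker for Tables 11.1.1 and 11.2.1. Their selection cannot be sized from the documents, and labelling them as conditional would be a defensible alternative to replacing them.

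**Conclusion.** The concern holds as a minor defect. That PP 6-month survival equals 1.0000 with everyone at risk follows from the definitions alone, with the single exception for mislabelled visits. The PP 12-month row and log-rank test rest only on deaths after the 9-month VAS. The clash between 10.2 with its tables and 10.2.7 with its figures is explicit and unresolved.

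The size of the gap depends on assumed mortality and a constant hazard: across m = 10% to 45%, 6-month mortality differs by about 5 to 26 percentage points between all treated subjects and PP. The documents do not show that the gap will appear in this trial, and they give no direction of bias between arms. The primary VAS analysis is not touched by this point.

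**What to change.** 1. Exempt 10.2.7 from the population sentence in SAP 10.2.
2. Replace PP Tables 11.1.1, 11.2.1 and 11.3.1 with Safety-population tables by treatment received, matching 10.2.7 and Figures 1 to 3. If a PP version is kept, label it as conditional on reaching the 9-month VAS.
3. Keep Tables 11.1.2, 11.2.2 and 11.3.2 as supportive. Because time runs from first dose, label them as treated subjects analyzed as randomized, and add a row counting subjects randomized but never treated.

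The cost is one sentence in 10.2, the population and arm rule of three tables, and a label and count row in three more. No new data are needed: the Safety population, the time origin and the first-dose date (Listing 1) are already specified, and the figures stay as they are. The change should be made before unblinding.

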10.2.1. VISUAL ANALOGUE SCALE FOR PAIN (VAS)

The VAS measurements, change from baseline and percent change from baseline will be summarized at each visit by treatment arm using the methods described in Section 10.1.

Categorical analysis of VAS measurements will be performed by visit. Each VAS measurement will be assigned to one of the following 4 categories: 0-4 mm, 5-44 mm, 45-74 mm and 75-100 mm. Incidence and percentage of each VAS category will be presented for Baseline and each post baseline visit. Testing for treatment differences versus placebo will be carried out using a CMH test (Row Means Score).

10.2.1.1 Imputation Methods of VAS Results for the ITT Population

For subjects without the efficacy endpoint (VAS change from baseline to any post baseline result), the following imputation methods will be applied:

- For missing Baseline VAS, assign the VAS score at Screening if the VAS score at Day 0 is missing.
- For any post baseline VAS, assign the post baseline VAS score prior to the missing post baseline VAS via the last observation carried forward (LOCF) method.

For subjects who had a major amputation or limb procedure carried out, the following imputation methods will be applied:

- For subjects with a major amputation, assign the VAS score prior to the amputation.
- For subjects with a limb salvage, assign the VAS score prior to the intervention.

10.2.2. TRANSCUTANEOUS OXYGEN PRESSURE ASSESSMENT (TcPO₂, MMHG)

Transcutaneous oxygen pressure measurements (tissue oxygenation) will be measured at the anterior calf, posterior calf, dorsum foot and chest. TcPO₂ measurements and change from baseline (= post-treatment – baseline) for each body region will be summarized by study visit and treatment arm using the method for continuous variables. The baseline value is the measurement taken at the Day 0 (Pre-Dose) Visit if the percent difference ($=|Day\ 0 - Screening|/Screening \times 100\%$) between the measurements taken at the Screening Visit and the Day 0 Visit is $\leq 15\%$. Otherwise, the baseline value is the average of the measurements taken at Screening and Day 0 Visits.

Additionally, TcPO₂ ratio for each of the body region (anterior calf, posterior calf, and dorsum foot) to chest will be calculated for each subject as TcPO₂ at each body region divided by the TcPO₂ at chest. The chest value to be used as the denominator when generating the TcPO₂ ratio for each of the body region will be by subject and calculated by taking the average of that subject's non-missing chest results reported at Day 0, Day 180, Day 270 and Day 365. Note: based on clinical input, chest values of less than 30 mmHg and greater than 95 mmHg should not be used for the purpose of assigning chest value averages. Therefore, such values will not be considered for TcPO₂ ratio determination. Supplemental analyses using such values may be generated for exploratory purposes. The change in the TcPO₂ ratio from baseline will also be calculated. The TcPO₂ ratio and the change in TcPO₂ from baseline will be summarized by study visit and study arm using the method for continuous variables.

10.2.2.1 Imputation Methods of TcPO₂ Results for the ITT Population

For subjects without the efficacy endpoint (TcPO₂ change from baseline to any post baseline result), the following imputation methods will be applied:

- For missing Baseline TcPO₂, assign the TcPO₂ score at Screening if the TcPO₂ score at Day 0 is missing.
- For any post baseline TcPO₂, assign the post baseline TcPO₂ score prior to the missing post baseline TcPO₂ via the last observation carried forward (LOCF) method.

For subjects who had a major amputation or limb procedure carried out, the following imputation methods will be applied:

- For subjects with a major amputation, assign the TcPO₂ score prior to the amputation.
- For subjects with a limb salvage, assign the TcPO₂ score prior to the intervention.

10.2.3. HEMODYNAMIC ASSESSMENTS (ABI/TBI)

Hemodynamic assessments taken on the index limb and contra-lateral limb include the following:

- Resting Ankle Brachial-Index (ABI) – measurements taken on both legs.
- Resting Toe Brachial-Index (TBI) – measurements taken on toe of right and left foot.

Resting ABI and TBI and the change from baseline (= post-treatment – baseline) will be summarized by index/non-index limb, study visit, and treatment arm using the method for continuous variables. A value of 0 will be assigned if no pulse is reported. Same as the transcutaneous oxygen pressure measurements described in Section 10.2.2, the baseline value is the measurement taken at the Day-0 (Pre-Dose) Visit if the percent difference between the measurements taken at the Screening Visit and the Day-0 Visit is $\leq 15\%$. Otherwise, the baseline value is the average of the measurements taken at Screening and Day-0 Visits. The change in ABI and TBI from baseline will be summarized by study visit and study arm using the method for continuous variables. Supplemental analysis for exploratory purposes may be generated that does not consider subjects who have a baseline TBI/ABI between .9-1.3 mmHg.

10.2.3.1 Imputation Methods of ABI/TBI Results for the ITT Population

For subjects without the efficacy endpoint (ABI/TBI change from baseline to any post baseline result), the following imputation methods will be applied:

- For missing Baseline ABI/TBI, assign the ABI/TBI score at Screening if the ABI/TBI score score at Day 0 is missing.
- For any post baseline ABI/TBI, assign the post baseline ABI/TBI score prior to the missing post baseline ABI/TBI via the last observation carried forward (LOCF) method.

For subjects who had a major amputation or limb procedure carried out, the following imputation methods will be applied:

- For subjects with a major amputation, assign the ABI/TBI score prior to the amputation.
- For subjects with a limb salvage, assign the ABI/TBI score prior to the intervention.

10.2.4. HIGH RESOLUTION MRA

The quantitative blood flow of the occluded target artery and the volumetric analysis of the newly developed artery will be recorded on a CRF for selected sites. The perfusion data at baseline, 6 months, and 9 months, and the change in perfusion from baseline to 6 and 9 months will be summarized descriptively using method for continuous variables at baseline, 6 months, and 9 months. The descriptive summaries will be provided by the independent laboratory. No statistical tests will be performed.

